8. Marcello Di Martino, Javier García Septiem, Rocío Maqueda González, Jose Luis Muñoz de Nova, Ángela de la Hoz Rodriguez, Alba Correa Bonito, Elena Martín, Pérez. Cirugía electiva durante la pandemia por SARS-CoV-2 (COVID-19): análisis de morbimortalidad y recomendaciones sobre priorización de los pacientes y medidas de seguridad. Cirugía Española. 2020.

Hypothesis:

At Bellvitge University Hospital (HUB), a specific circuit was created in order to keep the emergent and the scheduled surgical activity that cannot be delayed, following measures of security established during the pandemic. We consider that this measures have contributed to contain the rate of infection of these patients and the post-operative complications that have occurred during the maximum crisis period, generating a control of quality of care and security.

For this reason, the sample of operated patients will be compared with a sample of patients adjusted to the month of January, before the crisis of the pandemic.

As a working hypothesis, we consider that there are no differences, and therefore, we propose the study as a non inferiority in terms of the assistance results.

Objective:

Our objectives are:

1. Assess all patients who have underwent surgery in our hospital during the period of maximum crisis of the pandemic, from March 11, 2020 to May 15, 2020.
2. Determine the post-surgical complications that have occurred during this period.
3. Determine the rate of COVID-19 infections in these patients and the secondary complications generated by them.
4. Be able to compare with series adjusted for types of surgery, characteristics of the surgery, age and sex in the pre-pandemic period (January 2020).
5. Propose some potential improvements in the context of the health crisis

Methodology:

Design and sample size:

Observational study, that includes all patients who have undergone emergent or scheduled surgery from March 11th 2020 until May 15th 2020, with a total of 789 surgical interventions recorded during this period.

Data collection:

Our source of information will be basically the access to the virtual clinical history (SAP) of the patients and the closing of the episode according to the Minimum Data Set (MDS). Only data of

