interest for this research will be obtained, and in any cases, data that can be directly linked to patients (name, address, telephone number, etc.) will be used, preserving the confidentiality of the data. The variables of interest to be extracted from the clinical history to configure our data base will be:

- Age.
- Sex.
- Functional State according to ECOG (available in the annex).
- Personal antecedents of interest.
- Diagnosis of the pathology to be operated.
- Day of surgery.
- Type of surgery:
 - Specialty: general surgery, thoracic surgery, traumatology, neurosurgery, vascular surgery, neck and face surgery, urology...
 - If it consists on an emergent surgery or a scheduled surgery.
 - Delayable (benign) or non-delayable (malignant) surgery.
- Postoperative complications according to Clavien Dindo classification (available in the annex).
- Infection by COVID-19?
- Date of confirmation of the SARS-CoV-2.
- Treatment required by SARS; determined by groups.
- Hospital stay in days.
- Mortality.
- To assess the severity of the COVID-19 infection, we will use the Brescia Respiratory COVID19 Severity Scale (available in the annex).
- In addition, we will evaluate the therapeutic measures applied in each patient in case of COVID-19 infection (available in the annex).

Exclusion criteria:

1. Surgeries related to complications in the treatment of COVID patients.
2. Patients with incomplete data.

Selection criteria of the control sample (January 2020):

The selection will be made according to the type of surgery, sex and age range. In order to ensure that the sample is not inferior, the procedures chosen will be analysed with a ratio of 2:1 and 1:1 for patients undergoing emergent surgery, using as a reference the patients included during the COVID19 period, according to the list elaborated by Surgical Planification Department, where no operating results have been recorded (blind).

Statistical treatment:

It is considered a non-inferiority study, with a maximum difference in the percentage of patients with complications according to the Clavien Dindo classification of 10% and 2% in the percentage of patients with death result.

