A descriptive analysis will be carried out using the usual statistical tests: Chi-square test to compare the category variables, and the subtraction of variables using parametric or non-parametric tests for the continuous variables (depending on the normality of the variables). For all the variables, bilateral tests with a significance level of 5% will be used.

It should be noted that the results will be analysed after the selection of patients included.

Possible limitations of the study:

The retrospective aspect of the study will limit the value of the study. There may be a lack of information about some interesting facts in the clinical history in the postoperative follow-up after the surgical episode at the HUB. In case that some important information is required and not reflected in the Shared Clinical History of Catalonia, it could be completed by telephone contact with patient and/or relatives to avoid information bias. In case of not having it, it will be treated as "missing data" in the subsequent analysis of the data.

Expected Benefits of the Project:

The comparison with the previous cohort will help us to know if there has been a higher rate of morbidity and mortality.

We will also analyse the rate of infection by COVID-19 in post-operative patients during this period of time.

This will allow us to know the complications and infections that occurred during this period of pandemic and we will be able to search and discover avoidable situations and establish our own circuits and protocols to avoid them in the future.

It will help us to establish a quality control in our centre, because, since now, it will be necessary to coexist with COVID-19 for an undetermined period of time (infections still happen daily and, by the moment, there is not a treatment or an effective vaccine to eradicate it)

If we are able to identify the weak points of our system, if they are detected, we will avoid repercussions on the health of our patients and we will adapt our health resources better.

Ethical Aspects:

As we have already mentioned, only data of interest will be obtained for the research and, in any cases, we will use data that can be directly related to the patients (names, surname, address, telephone numbers...) in order to keep the confidentiality of the data.

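### Two non-inferiority margins (10 points for complications, 2 for death) serve one hypothesis, with no primary endpoint, no rule for a split result and no test against either margin

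*Combined protocol and SAP*

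**What the plan says.** The Hypothesis section sets a single hypothesis: "we propose the study as a non inferiority in terms of the assistance results". The Objective section lists five aims without ranking them.

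Under Methodology, the Statistical treatment section says "It is considered a non-inferiority study" and gives two limits in one sentence: the "maximum difference in the percentage of patients with complications according to the Clavien Dindo classification of 10% and 2% in the percentage of patients with" fatal outcome. It calls neither primary. It gives no testing order, no allocation of alpha and no conclusion for the case where one limit is met and the other is not.

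The same section then names the test, "Chi-square test to compare the category variables", and adds: "For all the variables, bilateral tests with a significance level of 5% will be used". It mentions no confidence interval and no test against a margin.

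The Expected Benefits section promises an answer on both outcomes: "The comparison with the previous cohort will help us to know if there has been a higher rate of morbidity and mortality". In the Annex (Figure 2), death is Clavien-Dindo grade V. No section says which grades count as a complication.

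**The concern.** The text fits three decision rules: both margins must be met, either suffices, or complications decide and death is secondary. These can give opposite verdicts on the same data. The endpoints are unequal. The 10-point limit is wide relative to the precision available, whereas the 2-point limit on a rare event is tight, so death is the more likely of the two to miss.

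The study is retrospective and its outcomes already exist. If the result splits, the summary verdict would be chosen after the data are seen. At stake is a non-inferiority statement, meant to inform the hospital's future circuits and protocols, that leaves a death excess above the plan's own limit unexcluded. The planned tests would not expose this, because a non-significant chi-square test does not show that a margin has been met.

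**Working it through.** **Nothing to reproduce.** The plan gives no power, planning rates or calculated sample size; 789 is a count of interventions.

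**Inputs from the documents.** Margins of 10 and 2 points, read as absolute differences; 789 pandemic cases; two-sided 5%, which for one margin is one-sided 2.5%.

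**Assumptions.**
- Complications 20–30% and death 1–3%. The only mortality figure in the plan, 1.7%, is respiratory-failure death in a cited cancer series, not a January rate.
- January patients: 395 (789/2), 789 or 1,578 (2 × 789), because the control-sample section does not say which side of its 2:1 ratio is the larger.
- Interventions are treated as patients, and deaths count as complications.
- A margin is met if the Wald upper limit, d + 1.96 × √[p₁(1−p₁)/n₁ + p₀(1−p₀)/n₀], lies below it.

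**Step 1: why the margins are unequal** (equal rates, 789 v 395; 1/789 + 1/395 = 0.003799).
- Complications 30%: SE = √(0.21 × 0.003799) = 2.82 points. The expected upper limit is 1.96 × 2.82 = 5.5 points, against 10. Power = Φ(10/2.82 − 1.96), about 94%.
- Death 1.7%: SE = √(0.0167 × 0.003799) = 0.80 points. The expected upper limit is 1.96 × 0.80 = 1.6 points, against 2. Power is about 71%.

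**Step 2: a concrete split.**
- Complications 237/789 v 118/395: 30.04% − 29.87% = 0.16 points, SE 2.82, upper limit 5.7 points. Met.
- Deaths 24/789 v 7/395: 3.04% − 1.77% = 1.27 points, SE 0.90, upper limit 3.0 points. Not met.
- The planned chi-square test on those deaths gives p of about 0.20 (no continuity correction), so it flags nothing.

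**Step 3: how often the endpoints disagree with no true difference** (200,000 simulated studies per scenario).

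| Death rate | 395 or 789 controls | 1,578 controls |
|---|---|---|
| 1% | 3–10% | 1–2% |
| 1.7% | 14–26% | 8% |
| 3% | 35–51% | not needed for the range |

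**Step 4: deaths truly higher** (395 or 789 controls, complications 20–30% in January).

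| True excess | Complications alone pass | Both pass |
|---|---|---|
| Deaths +2, total complications equal | 95–99.9% | 2–3% |
| Deaths +2, added to complications | 81–97% | 2–3% |
| Deaths +4, added to complications (death 1.7%) | 56–82% | about 0% |

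The first row requires non-fatal complications to fall by 2 points, since deaths are part of the total.

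**Step 5: error rate of each rule when both true differences sit at their margins.** If either margin suffices, the false-claim rate is 1 − Φ₂(1.96, 1.96; ρ): 4.9% at ρ = 0, 4.5% at 0.5 and 3.5% at 0.9, against 2.5% for one test. If both are required, it cannot exceed that of a single test, so no alpha split is needed.

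**The case against.** The strongest reply is that one sentence sets both limits for one study, so its most natural reading is that both apply. Nothing in the text positively supports an either-margin rule. Mortality has its own limit and is reported, so only the summary label is in doubt. This stands as a limit on the point: a reader might infer that the plan lets complications alone decide, but no passage says so. It does not close the gap, because joining two limits in a list does not say what follows when one is missed. The stated aim of the study also centres on complications, so treating death as secondary is not a strained reading.

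A reader might also infer that an overall claim is almost certain when deaths rise. That holds only if total complications stay equal while deaths rise. When the extra deaths add to complications, the figures drop as in Step 4. If complications rise by 5 points and deaths by 2, success under an either-margin rule is 42–67% (death 1.7%); with rises of 8 and 4 points it is 10–15%.

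Nor is a split the likely result. At 1.7% death with no true difference, agreement is the more common outcome, and disagreement reaches about half only at 3% death with 395 controls.

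Finally, these error rates describe a confidence-limit procedure that the plan does not contain. That is correct, and it is part of the point: the combining rule and the missing margin test need to be supplied together.

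**Conclusion.** The point holds as an unresolved decision rule. Two margins serve one hypothesis, no primary endpoint is named, a split result has no stated conclusion, and the planned tests address neither margin. This follows from the text and needs no assumed rates.

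Its size does depend on assumed rates and on the unclear control ratio. Across the assumptions above, the endpoints disagree in about 1–51% of studies with no true difference. With 395 or 789 controls and deaths 2 points higher, complications alone would pass in 81–99.9%, depending on whether the extra deaths add to complications, against 2–3% if both margins are required. The documents support saying that a non-inferiority claim could be made with excess death not excluded. They do not support saying that the plan intends this, or that it is the expected result. The change should be made; confidence is medium because the January rates are unknown.

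**What to change.** **In Statistical treatment, at the sentence with the two margins**, state: Complications and death are co-primary. Non-inferiority of the pandemic period is concluded only if the upper limit of the two-sided 95% confidence interval for the difference (pandemic minus January) is below 10 percentage points for complications and also below 2 percentage points for death. No alpha adjustment is needed because both must be met. If only one is met, that endpoint is reported alone and no overall non-inferiority is claimed.

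**At the sentence on chi-square tests**, add that these tests and all other comparisons are descriptive and do not support the non-inferiority conclusion.

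**Define a complication** by stating which Clavien-Dindo grades count, so that the first margin has a fixed meaning.

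A fixed testing order that makes any overall claim conditional on the death margin would also close the gap.

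**Cost.** A few sentences of wording; no new data or patients. The joint claim is harder to reach: with no true difference, death at 1.7% and 395 or 789 controls, success is about 72–86%, against 98–100% if either margin sufficed. The difference comes only from requiring the mortality criterion.

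### Chi-square is the only test named for categorical variables, so a comparison of Clavien-Dindo grades between periods would ignore their order and lose power to detect a change in complication severity

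*Combined protocol and SAP*

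**What the plan says.** Under Methodology, Data collection, the plan lists "Postoperative complications according to Clavien Dindo classification (available in the annex") as a variable. Figure 2 of the annex gives grades I, II, IIIa, IIIb, IVa, IVb and V, ranked by the treatment that the complication required. Adding "no complication" makes six levels, or eight with sub-grades.

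Under Methodology, Statistical treatment:
- The study is framed as non-inferiority on two percentages: patients with complications (margin 10%) and deaths (margin 2%).
- The tests are introduced thus: "A descriptive analysis will be carried out using the usual statistical tests".
- For categorical data the method is "Chi-square test to compare the category variables".
- The alternative, "parametric or non-parametric tests for the continuous variables", is limited to continuous variables.
- On error rates: "For all the variables, bilateral tests with a significance level of 5% will be used".

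No method for ordered scales is named. Nor does the plan say how Clavien-Dindo will be tabulated: any or none, minor or major, main grades, or sub-grades.

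**The concern.** The Pearson chi-square gives the same result if the grades are relabelled in any order. A consistent move towards worse grades is therefore spread over 5 degrees of freedom (six levels) or 7 (eight levels), where an ordinal test concentrates it on one.

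This matters because the any-complication percentage counts a grade I deviation the same as multi-organ failure. Between that percentage and death, the grade is the plan's only measure of how severe complications were in both periods. The working hypothesis is no difference, so a non-significant result from a weak test leans towards the expected conclusion.

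**Working it through.** The plan states no power, no expected rates and no grade distribution, and 789 is a count of interventions. There is no figure of the plan's to reproduce, so the size of the loss has to be shown over assumptions.

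**Inputs from the documents.** 789 interventions in the pandemic period; two-sided 5% tests; controls at 2:1, and 1:1 for emergent surgery.

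**Assumptions.**
- Controls: the direction of the 2:1 ratio and the emergent share are not given, so the range is 395 (789/2) to 1578 (2 × 789).
- January complication rate: 15%, 25% or 35%.
- Split among complicated patients: I 35%, II 33%, IIIa 6%, IIIb 12%, IVa 6%, IVb 2%, V 6%.
- Common odds ratio for a shift along the whole scale: 1.3 or 1.4.

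**Step 1: one case by formula.** Take 25% complications, six levels, 789 v 789, odds ratio 1.3. The any-complication odds go from 0.25/0.75 = 0.333 to 0.433, a rate of 0.433/1.433 = 0.302. Applying the odds ratio at every cut gives, for none, I, II, III, IV, V:
- January: 0.7500, 0.0875, 0.0825, 0.0450, 0.0200, 0.0150
- Pandemic: 0.6977, 0.1009, 0.0999, 0.0565, 0.0256, 0.0194

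With equal groups the chi-square noncentrality is 789 × Σ (difference)² / (sum of the two proportions) = 789 × (0.00189 + 0.00095 + 0.00165 + 0.00131 + 0.00069 + 0.00057) = 789 × 0.00706 ≈ 5.6. On 5 degrees of freedom that gives power of about 0.40. The same noncentrality on 1 degree of freedom gives about 0.66, the power of the Wilcoxon test here.

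**Step 2: simulation, 20,000 tables per setting, 25% complications.**

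| Controls | Odds ratio | Chi-square, 6 levels | Chi-square, 8 levels | Wilcoxon, all patients | Any complication (binary) |
|---|---|---|---|---|---|
| 395 | 1.3 | 0.24 | 0.19 | 0.48 | 0.47 |
| 395 | 1.4 | 0.41 | 0.34 | 0.70 | 0.69 |
| 789 | 1.3 | 0.40 | 0.35 | 0.66 | 0.64 |
| 789 | 1.4 | 0.64 | 0.58 | 0.86 | 0.85 |
| 1578 | 1.3 | 0.55 | 0.50 | 0.78 | 0.77 |
| 1578 | 1.4 | 0.81 | 0.76 | 0.94 | 0.94 |

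Over complication rates of 15% to 35% the gap between chi-square and Wilcoxon runs from about 10 to 35 points.

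**Step 3: severity changes, but the complication rate does not.** Hold the rate at 25% and shift the grades only among complicated patients (0.25 × 789 ≈ 197 per period), with five main grades among them.

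| Odds ratio among complicated | Chi-square, all patients | Wilcoxon, all patients | Chi-square, complicated only | Wilcoxon, complicated only |
|---|---|---|---|---|
| 1.5 | 0.36 | 0.07 | 0.39 | 0.61 |
| 2.0 | 0.85 | 0.09 | 0.88 | 0.97 |

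The ordinal test is the strongest of the four when it is restricted to complicated patients. Applied to all patients it nearly misses this kind of change, because 75% of patients are tied at "none" in both periods.

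**The case against.** The strongest reply is that the plan's criteria are two binary percentages, to which order is irrelevant, and that the chi-square belongs to an analysis described as descriptive. For a shift along the whole scale, the any-complication comparison already has nearly the power of the Wilcoxon test (0.64 against 0.66 in the example), so the study would not miss such a shift. Swapping chi-square for an all-patient Wilcoxon test could even do harm (0.85 down to 0.09 in step 3). All of this stands. It makes the point secondary and decides the form of the remedy. It does not defend an order-blind test for comparing severity: among complicated patients the ordinal test gains 9 to 22 points at 197 per period.

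Three stronger readings are tempting, and the documents do not support them.
- *That the plan commits to an order-blind test of the full grade table as its main evidence.* It never says that the full grades will be tested. This follows only by default from one general sentence, and the named criteria are the two percentages.
- *That functional status is a second ordered outcome put at risk.* The entry "Functional State according to ECOG (available in the annex") stands with age, sex and history, so it reads as a patient characteristic. Power to detect worse complications does not apply to it.
- *That sparse cells make the chi-square invalid.* With six levels, 25% complications and 789 per period, the smallest expected count under no difference is 0.06 × 0.25 × 789 = 11.8. Counts below 5 arise mainly with sub-grades (IVb: 0.02 × 0.25 × 789 = 3.9), and simulated type I error stays at 0.044 to 0.051.

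**Conclusion.** The point holds for a secondary analysis. As written, a between-period comparison of Clavien-Dindo grade falls to a test that ignores order. The loss against an ordinal test is roughly 10 to 35 points of power for a whole-scale shift. For a change confined to severity it is 22 points at odds ratio 1.5 and 9 at odds ratio 2.0, among 197 complicated patients per period. Every figure rests on the assumed complication rates, grade split, odds ratios and control numbers. The direction would hold for any consistent move towards worse grades, provided that the ordinal test is run in the right set of patients.

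The 10% and 2% non-inferiority criteria are not affected, and a reader should not infer that the main conclusions fail on this ground. The result bears on how far a non-significant grade comparison can be read as evidence that complications were no more severe.

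**What to change.** In Statistical treatment:
1. Keep the any-complication and death percentages as the main comparisons, and keep chi-square for unordered variables such as sex and specialty.
2. Fix the Clavien-Dindo levels in advance (main grades or sub-grades).
3. Compare grade between periods among patients with a complication, by a tie-corrected Wilcoxon test or a proportional-odds model giving a common odds ratio with 95% confidence interval.
4. Report the same ordinal comparison in all patients, with "none" as the lowest level, beside it. Label both as secondary.

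The cost is a few sentences and no new data. There are small downsides. The complicated-only comparison conditions on having had a complication, so the two groups may differ in who enters it. The all-patient version is weak for a pure severity shift. The common odds ratio assumes proportional odds. These are the reasons to report both and to rest on neither alone.

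### The 10-point and 2-point non-inferiority margins enter no stated analysis: the only test named for complications and death is a two-sided chi-square of no difference

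*Combined protocol and SAP*

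**What the plan says.** The Hypothesis section frames the comparison with January 2020 this way: "we consider that there are no differences, and therefore, we propose the study as a non inferiority in terms of the assistance results".

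'Statistical treatment' opens with the margins: "It is considered a non-inferiority study, with a maximum difference in the percentage of patients with complications", graded by Clavien-Dindo, "of 10% and 2% in the percentage of patients with death result".

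The same section then gives the whole analysis: "A descriptive analysis will be carried out using the usual statistical tests: Chi-square test to compare the category variables", parametric or non-parametric tests for continuous variables, and "For all the variables, bilateral tests with a significance level of 5% will be used".

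The margins are not mentioned again. No section names a confidence interval, a test against a non-zero difference, or the result that would count as non-inferior.

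Two design facts bear on the remedy. For the January controls, "The selection will be made according to the type of surgery, sex and age range", and procedures are "analysed with a ratio of 2:1 and 1:1 for patients undergoing emergent surgery". The COVID-period group is a count of what took place, "with a total of 789 surgical interventions recorded during this period", and not a calculated sample size.

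**The concern.** A non-inferiority analysis has to reject the hypothesis that the COVID-period rate exceeds the January rate by the margin or more. The chi-square has a different null, equality of the two rates, and gives the same p-value whether the margin is 2 points or 20. Followed as written, the plan never tests its own hypothesis, and the rule for claiming non-inferiority would have to be chosen at analysis.

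The likely substitute is to read a non-significant p-value as support. The plan does not say this. However, it moves straight from an expectation of no differences to a non-inferiority design and offers no other rule, which makes that reading easy. Low power then works in favour of the claim: the fewer the deaths or controls, the more readily a real excess goes undetected and is reported as acceptable.

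Two-sided testing at 5% is not itself the error, since it corresponds to a two-sided 95% interval.

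**Working it through.** The plan states no power, event rate or calculated sample size, so there is no figure of its own to reproduce.

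**Inputs from the plan:** margins of 10 and 2 points; two-sided 5%; 789 COVID-period interventions before exclusions; a control ratio of 2:1, or 1:1 for emergent surgery.

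**Assumptions:** the January rates; independent, unmatched groups; 789 controls unless stated otherwise. The direction of 2:1 and the emergent share are not given, so the control total could run from about 395 (789/2) to 1578 (789 × 2). The 1.7% in the background is respiratory-failure mortality in cancer patients operated on around the pandemic peak, and serves only as one point in the range.

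**Step 1. What each method tests.** Chi-square: z = (p₁ − p₀)/√[p̄(1 − p̄)(1/n₁ + 1/n₀)], where p̄ is the pooled rate. No margin appears. Non-inferiority: the upper 95% limit of p₁ − p₀ must be below the margin. The Newcombe upper limit is d + √[(u₁ − p₁)² + (p₀ − l₀)²], where d = p₁ − p₀ and u and l are Wilson limits.

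**Step 2. Deaths, 24/789 vs 13/789.**
- Rates 3.04% and 1.65%, d = 1.39 points.
- p̄ = 37/1578 = 0.02345; SE = √(0.02345 × 0.97655 × 2/789) = 0.00762; z = 1.83, p = 0.067.
- Wilson limits 2.05% to 4.49% and 0.97% to 2.80%.
- Upper limit = 1.39 + √(1.44² + 0.68²) = 2.99; the lower limit, by the matching formula, is −0.12.
- Not significant, yet the 2-point margin is not excluded.

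**Step 3. Complications, 197/789 vs 158/789.**
- Rates 24.97% and 20.03%, d = 4.94 points.
- p̄ = 355/1578 = 0.2250; SE = 0.02102; z = 2.35, p = 0.019.
- Upper limit = 4.94 + √(3.14² + 2.64²) = 9.05; lower 0.82.
- Significant, yet the 10-point margin is met.

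**Step 4. How often this happens.** Simulation with 400,000 draws per scenario, chi-square without continuity correction, Newcombe limit.

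Death, 789 vs 789:

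| January rate | True rise 2 points: chi-square non-significant | No true difference: upper limit below 2 points |
|---|---|---|
| 0.5% | 6% | >99% |
| 1% | 17% | 95% |
| 1.7% | 30% | 83% |
| 3% | 47% | 62% |
| 5% | 61% | 44% |

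With the true rise equal to the margin, the confidence-limit rule wrongly passes 2% to 3% throughout.

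Hand check at 1.7% vs 3.7%: the null SE is √(2 × 0.027 × 0.973/789) = 0.00816 and the alternative SE is √[(0.017 × 0.983 + 0.037 × 0.963)/789] = 0.00815. P(non-significant) ≈ Φ[(1.96 × 0.00816 − 0.02)/0.00815] = Φ(−0.49) ≈ 0.31, against 0.296 simulated.

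Complications, 789 vs 789, true rise 5 points: chi-square is significant for harm while the upper limit is below 10 points in 70%, 33%, 13% and 4% of studies at January rates of 10%, 20%, 30% and 40%.

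**Step 5. Sensitivity to size.** With 700 vs 700, the chi-square column for death becomes 9%, 21%, 35%, 51% and 65%. At a 1.7% January rate it is 51% with 395 controls, 30% with 789 and about one in six with 1578.

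**The case against.** The best defence is that the analysis text describes itself as descriptive. On that reading the chi-square sentence covers the tables, the margin comparison was simply left unwritten, and two-sided 5% points towards a 95% interval. The plan also says, under 'Expected Benefits of the Project', that the comparison will show whether morbidity and mortality were higher, and a two-sided test suits that question. This is a fair account of how the gap may have arisen, but it does not fill it. The margins have no analysis on either reading. The phrase about a maximum difference does not say whether the point estimate or a confidence limit must fall below the margin, and the choice matters: 20 vs 13 deaths in 789 each gives a difference of 0.9 points, under the margin, with a Newcombe upper limit of 2.4, above it.

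Three narrower points stand.
- The complications example is not a contradiction. A rate can be higher than January's and still within 10 points; the two methods answer different questions.
- False reassurance is mainly a problem for death. For complications with a true 10-point rise and 789 per group, chi-square is non-significant in about 2% of studies or fewer at January rates of 10% to 40%.
- Equal totals would follow from the stated ratios only if every case were emergent, so the percentages are illustrations across a range.

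**Conclusion.** The concern holds and should be corrected before the data are analysed. The plan declares non-inferiority, fixes two margins, and then specifies only a test that ignores them. This follows from the text alone and needs no assumed rate.

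The size of the consequence does rest on assumptions. If non-significance were taken as success, a true 2-point rise in deaths would be passed in 6% to 61% of studies with 789 per group, depending on the January rate, against 2% to 3% under a confidence-limit rule. Fewer controls make this worse and more controls make it better. For complications the main risk runs the other way: a significant chi-square could be read as failure when the margin is in fact met.

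**What to change.** In 'Statistical treatment':

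- Make the main analysis of each margin endpoint the risk difference, COVID period minus January, with a two-sided 95% confidence interval.
- Account for the selection by type of surgery, sex and age range and for the different ratio in emergent cases. A stratified Miettinen-Nurminen or Mantel-Haenszel risk difference would do, with an unstratified Newcombe interval as a check. Other estimators that respect the selection are acceptable.
- Conclude non-inferiority for an endpoint only if its upper limit is below 10 points (complications) or 2 points (death).
- State in advance whether the overall claim needs both endpoints or is made for each separately. If both are required, no split of alpha is needed.
- Keep chi-square for the descriptive tables, and state that a non-significant p-value is not evidence of non-inferiority.

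To make this executable, also say which Clavien-Dindo grades make a patient count as having a complication, and which group is the 2 in the 2:1 ratio.

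The cost is a few sentences and no new data, but also candour about death. With no true difference and 789 per group, power for the 2-point margin is 95% at a 1% death rate, 83% at 1.7%, 62% at 3% and 44% at 5%. At 1.7% it is 77% with 395 controls and 87% with 1578. The plan should say that non-inferiority for death may not be demonstrable. Power for the 10-point margin is at least 98% at complication rates of 20% to 40% with equal groups, and 92% at a 40% rate with 395 controls.
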